### 8.3.1 Investigational medicinal product Stock Lists (Drug Accountability)

The investigator/pharmacist, or another appropriate individual who is designated by the investigator, should maintain records of the stocks of the investigational medicinal product or its disposal.

- Each delivery will be documented in writing on the forms provided and the forms will be returned to the Drug Distribution Center stated as an acknowledgement of receipt.
- Complete documentation of the whereabouts of the investigational medicinal product (incoming/outgoing) on appropriate forms is mandatory. These records should include dates, quantities, batch numbers, expiry dates (if applicable) and the unique code numbers assigned to the investigational medicinal product and the trial subjects. The investigator should maintain records that document adequately that the subjects received the doses specified by the protocol. These records should be checked against all delivery notes received from Novartis.
- Reasons must be given for stock deficiencies.
- The Investigator is responsible for destroying any unused, partially used and empty investigational medicinal product after the clinical monitor has approved the drug accountability logs. This process should be documented appropriately. A confirmation of the destruction will be sent to the Drug Distribution Center.
- The patients should only receive two medication kits at a time.
- The patients should document the administration of the study drug in a patient diary which will be provided from the sponsor.

## 8.4 Route of Administration Toxicities and Drug Interactions

### 8.4.1 Route of Administration

Midostaurin will be administered orally twice daily according to the schedule in the Treatment Plan. Patients should take their daily dose at approximately the same time each day, and separated by approximately 12 hours between the morning and evening doses. Each daily dose should be given with food and a glass of water (approx. 240 ml).

### 8.4.2 Toxicities

When given as a single agent, doses of up to 300 mg per day (100 mg three times a day) of midostaurin have been used. A dose of 225 mg per day (75 mg three times a day) was originally selected for phase II studies. The adverse events most frequently reported and considered related to midostaurin were nausea, vomiting, and fatigue. In most cases vomiting occurred within an hour of taking midostaurin and subsided when treatment was withdrawn. Treatment with antiemetics was tried with variable success. Other adverse events commonly reported and suspected to be related to midostaurin include headache, and diarrhea. Serious adverse events considered related to midostaurin include diarrhea, vomiting, nausea, anorexia, anemia, leukopenia, elevated liver transaminase levels, and pulmonary edema.

The tolerability (MTD) of midostaurin in combination with chemotherapy is somewhat lower than that seen with single agent midostaurin due to additive toxicity of nausea and vomiting in the combination regimens.

Reversible elevations in transaminases and bilirubin have been reported with midostaurin, including at least three patients with grade 3 elevations at the 50 mg BID dose. To date, there have been no associated pathological changes reported. Transient increase in serum amylase of unknown significance has been observed in four oncology patients. Rash (grad 3 / 4) also was reported in at least one patient.

Pulmonary toxicity including fatal pulmonary events have been described in patients receiving midostaurin. It hast been suggested that pulmonary toxicity may be associated with co-administration of azole antifungal drugs and resultant inhibition of CYP3A4.

Two cases of hyperthyroidism were reported as serious adverse events in two patients treated with midostaurin in combination with imatinib for imatinib-resistant gastrointestinal tumors (GIST). Additionally, there were two adverse events of grade 1 and grade 2 hyperthyroidism as well as six events of asymptomatic thyroid function test lab changes reported in the same study. It is felt that theses events were possibly related to the combination study medication although the mechanism

is not clear. To date, trials with midostaurin monotherapy have not yielded any reports of hyperthyroidism or similarly mentioned thyroid function test abnormalities.

### 8.4.3 Drug interactions

Midostaurin is metabolized by CYP3A4 to active compounds. As described in section 7.3, potent CYP3A4 inhibitors are thought to represent the most significant potential for drug interactions with midostaurin.

## 9 Endpoints for the Assessment of Efficacy and Safety

### 9.1 Efficacy

As pointed out in section 2.1, the reduction of overall survival in patients with c-KITmut is mainly due to a higher incidence of relapses while in FLT3-ITD patients, primary resistant disease leads to the inferior prognosis during the early course of the disease. Since the patient group in this trial consists both of c-KITmut and FLT3-ITD patients, event-free survival seems to be the measure to capture both early treatment failure in FLT3-ITD and later relapse from CR in c-KITmut patients. Therefore, the primary study endpoint will be the event-free-survival (EFS) rate at 2 years. Event-free survival will be defined as the time from inclusion in the study (date of signed informed consent) until either failure to achieve a CR/CRi five weeks after the beginning of the second induction therapy course), or hematological relapse from CR/CRi, or death from any cause. Revised IWG criteria will be used [17].

### 9.1.1 Complete Remission (CR):

Complete remission is defined as the presence of all of the following:

Peripheral Blood Counts

- Absolute neutrophil count ≥1000/µL.
- Platelet count  $\geq$  100,000/µL.
- No leukemic blasts in the peripheral blood.
- Transfusion independence for red cells and platelets.

#### Bone Marrow

- Adequate cellularity for assessment with maturation of all cell lines.
- No Auer rods.
- < 5% blast cells.

No extramedullary leukemia (such as CNS or soft tissue involvement),

### 9.1.2 Complete Response with incomplete blood count recovery (CRi):

CRi satisfies all CR criteria except platelet counts are < 100,000/µL or ANC < 1,000/µL

#### 9.1.3 Relapse

### Any of the following, occurring after either CR or (CRi):

- The reappearance of circulating blast cells on more than one determination
- >5% AML blasts in the bone marrow, not attributable no another cause (e.g. bone marrow regeneration). If there are no circulating blasts, but the marrow contains 5%-20% blasts, a repeat marrow ≥ 1 week later with >5% blasts is necessary to meet the criteria for relapse.
- Development of extramedullary leukemia

### 9.2 Safety

#### Laboratory:

The following laboratory parameters will be used for the assessment of safety:

- Complete blood counts (CBC)
- Chemistry and Coagulation
- Urinalysis

#### Clinical:

- Clinical examination including
- blood pressure
- pulse

### ECG and Echocardiography

The ECG recordings for the assessment of safety will be performed as 12-lead standard ECGs. Echocardiography assessment will be done for the determination of LVEF in M-Mode technique.

### Further safety examinations

A regular toxicity assessment will be obtained as outlined in the study evaluations (7.4) and in chapter 10. Furthermore, the primary endpoint of this trial, event-free survival is a combined efficacy and safety endpoint and will therefore also be used for the assessment of safety.

## **10** Handling of Adverse Events (AEs)

### 10.1 Definition/Documentation of (Serious) Adverse Events

### 10.1.1 Definition and Documentation of AEs

An adverse event (AE) is any untoward medical occurrence in a patient or clinical investigation subject administered a pharmaceutical product and which does not necessarily have a causal

relationship with this treatment. An AE can therefore be any unfavourable and unintended sign (including an abnormal laboratory finding), symptom, or disease temporally associated with the use of a medicinal (investigational) product, whether or not related to the medicinal (investigational) product. In this context it must be especially stressed that any change in laboratory findings or vital functions, which leads to the discontinuation of the subject's treatment with the investigational medicinal product or to the termination of the clinical trial, must always be documented as an AE.

The investigator will monitor the development of adverse clinical events or pathological laboratory findings until recovery or stabilisation of the subject's condition.

Irrespective of any causal relationship, all adverse events spontaneously reported by the subject or observed by the investigator will be continuously documented in the medical record and on the designated case report form (AE form) during the clinical trial/at each follow-up visit. AEs will be documented from the first administration of study drug up to 30 days after the last administration. Classification of AEs will be done according to the CTC-AE classification, Version 3.0. Suspected relationship of between the AE and the study drug midostaurin or daunorubicin or cytarabine will be documented by the investigator.

### 10.1.2 Definition and Documentation of SAEs

A Serious Adverse Event (SAE) is any untoward medical occurrence that:

- results in the death of the subject,
- is life-threatening,
- requires inpatient hospitalisation of the trial subject or prolongation of existing hospitalisation,
- results in persistent or significant disability/incapacity, or
- is a congenital anomaly/birth defect.

Other conditions which, in the investigator's opinion, may not be immediately life-threatening or result in hospitalisation, but may jeopardise the subject's safety or may require intervention to prevent one of the other outcomes listed in the definition above, may also be considered serious. Examples of such conditions include: Allergic bronchospasm requiring treatment in an emergency room or at home; Unexpected convulsions (i.e. convulsions which cannot be explained by the underlying illness) that do not result in hospitalisation; Development of drug dependency or drug abuse, etc.

#### **Documentation**

All serious AEs (with the exception of the special situation described below) that occur during the study *or within 30 days* after the end of the subject's participation in the study will be documented on the SAE report form provided and the form will be passed on as described in the section below. The

end of the subject's participation in the study is defined as the end of follow up = the end-of-study visit.

### **10.2 Reporting Requirements for SAEs**

### 10.2.1 Investigator Requirements for Reporting SAEs

All SAEs must be reported by fax to the following address within 24 hours after knowledge:

MIDOKIT-Safety Desk SAL-Studienzentrale [name] 01307 Dresden *[contact]* [contact]

### 10.2.2 Sponsor Requirements for Reporting SAEs

#### SUSARs:

The sponsor's expedited reporting requirements are particularly relevant to suspected unexpected serious adverse reactions (SUSARs). The definition is a combination of the definitions of serious adverse reaction (adverse reaction that results in death, is life-threatening, requires insubject hospitalisation or prolongation of hospitalisation, results in persistent or significant disability/incapacity, causes congenital anomaly/birth defect) and unexpected adverse reaction (an adverse reaction, the nature or severity of which is not consistent with the applicable product information for the investigational medicinal product).

### **Reporting Requirements:**

The sponsor's reporting requirements are divided into **expedited** reporting and reporting that must be performed on request or annually. The sponsor's expedited reporting requirements comprise the following:

- All SUSARs must be reported within 15 days after knowledge (section 13, para. 2 GCP-V),
- All SUSARs that are life-threatening or result in death must be reported within 7 days after knowledge (section 13, para. 3 GCP-V),
- All circumstances requiring a review of the benefit/risk evaluation of the investigational medicinal product must be reported within 15 days after knowledge (e.g. expected serious adverse reaction with unexpected outcome, increased incidence of expected serious adverse reactions, SUSARs after the end of the subject's participation in the clinical trial, events in

connection with the study conduct or the development of the investigational medicinal product which may affect the safety of the trial subjects) (section 13, para. 4 GCP-V).

### Study specific reporting exceptions:

Leukemia-associated serious adverse events are excluded from expedited reporting on this protocol, but must be documented in the source data and the CRF. The events excluded from the time lines of expedited reporting are:

- fever resulting from AML progression
- infections resulting from AML progression
- bleeding resulting from AML progression
- hospitalization resulting from AML progression

AML progression is defined by re-appereance of peripheral blood blasts or appereance/ reappereance of chloromas or an increase in the BM blast count.

The following signs of hematotoxicity/ myelosuppression are intended and expected events during treatment of AML, do therefore not fulfil criteria of adverse events and do not need to be documented as AEs or SAEs:

- leukopenia
- thrombocytopenia
- anemia.

Myelosuppression-associated complications and related hospitalizations must be reported on appropriate pages of the CRF as an adverse event but are excluded from expedited reporting. These complications are:

- fever and infections resulting from leukopenia between the start of each cycle of chemotherapy and day 39 from start
- bleeding resulting from thrombopenia between the start of each cycle of chemotherapy and day 39 from start

In this context only prolonged myelosuppression, i.e. pancytopenia with marrow hypocellularity on day 40 or later from start of last cytotoxic therapy without evidence of leukemia, will require immediate reporting on an SAE form.

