### 6.3 Removal of patients from study

All patients reaching a primary efficacy endpoint of the trial (event) will discontinue study treatment and will be followed up until 25 months after study entry. The following events will lead to discontinuation of study treatment:

- Primary refractory disease, defined as failure to achieve a CR/CRi five weeks after the beginning of the second induction therapy
- Hematological relapse from CR/CRi
- Death from any cause

A patient who withdraws is one who discontinues participation in a clinical study for any reason. Patients may be withdrawn from the trial for the following reasons:

- At their own request or at the request of their legally acceptable representative
- If, in the investigator's opinion, continuation in the study would be detrimental to the patient's well-being
- At the specific request of the sponsor

Patients must be withdrawn also for the following reasons:

- In case of unacceptable toxicity or progressive disease
- In case of substantial non-compliance with the requirements of the study
- Positive beta-HCG test consistent with pregnancy. Pregnancy will be reported along the same time lines as a serious adverse event
- Use of illicit drugs or other substances that may, in the opinion of the investigator, have a reasonable chance of contributing to toxicity or otherwise skewing results
- Development of an intercurrent illness or situation which would, in the judgment of the investigator, affect assessments of clinical status and study endpoints to a significant degree
- Development of a second cancer that requires treatment
- Patient is lost to follow-up
- Period of > 64 days between the start of the last consolidation cycle and beginning of maintenance treatment
- Interruption in study drug administration for a period longer than 28 consecutive days during maintenance treatment

Relevant visit data will be entered into the CRF, and any unused study medication will be accounted for and returned for all subjects entered into the trial even if for a brief period of time. Subjects who discontinue study treatment will have relevant information completed and recorded in the CRF and medical record. All subjects who discontinue because of adverse events or clinical laboratory abnormalities should be followed up until they recover or stabilize and the subsequent outcome recorded.

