### **MidoHiDAC**

Cytarabine	3000 mg/m  IV over 3 hrs twice daily	days 1,3,5
Midostaurin	50 mg (2 capsules) p.o. twice daily	days 8-21

High-dose cytarabine (HiDAC) 3000 mg/m^2 will be given by intravenous infusion over 3 hours every 12 hours on days 1, 3, and 5. Serial neurologic evaluation will be performed before and following the infusion of high-dose cytarabine.

It is recommended to administer dexamethasone 0.1% or other corticosteroid ophthalmic solution 2 drops to each eye four times per day to begin 6-12 hours prior to the initiation of the cytarabine infusion and to continue for at least 24 hours after the last cytarbine dose.

Midostaurin 50 mg (two 25 mg capsules) is given twice a day by mouth on days 8-21. Midostaurin is not given from day 22 of the current cycle and day 7 of the next consolidation cycle. Patients should take their doses at approximately the same time each day, and approximately 12 hours should elapse between the morning and evening doses. Each daily dose should be given with food and a glass of water (approx. 240 ml). Patients should be instructed to swallow capsules whole and not chew capsules. If vomiting occurs, no re-dosing is allowed before the next scheduled dose.

For **remission assessment**, a bone marrow aspirate (or bone marrow biopsy) must be performed one week after recovery of ANC  $\geq$  1000/µL and platelets  $\geq$  100,000/µL to document a complete remission. Remission assessment must be performed latest 35 days after the beginning of each consolidation cycle, even if ANC or platelets are below the described threshold.

If remission assessment shows < 5% myeloid blasts, the patient has a sustained CR/CRi and will continue treatment according to this protocol.

If remission assessment reveals  $\geq$  5% myeloid blasts, the patient has a relapse from CR/CRi and will discontinue study treatment. Patients who discontinue study treatment will be followed up until 25 months after study entry.

At each bone marrow aspiration, material should be obtained and sent to the central SAL laboratory in Dresden for MRD diagnostics (see section 7.4).

Three cycles of MidoHiDAC shall be administered depending on adequate blood counts and sufficient organ function.

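### Section 10.2.2 defines AML progression so loosely that a serious event in a patient still in remission can be attributed to it and left out of expedited reporting

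*Protocol*

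**What the plan says.** Section 10.2.2 of the protocol, under the study-specific reporting exceptions, states: "Leukemia-associated serious adverse events are excluded from expedited reporting on this protocol, but must be documented in the source data and the CRF". It introduces the list of events with "The events excluded from the time lines of expedited reporting are" and then names four kinds: fever, infection, bleeding and hospitalisation, each on condition that it results from AML progression. It then defines AML progression as the return of blasts to the peripheral blood, or the appearance or "reappereance of chloromas or an increase in the BM blast count".

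The protocol classifies disease status differently elsewhere. Section 9.1.1 requires fewer than 5% marrow blasts for CR. In section 7.1 (MidoHiDAC), a remission assessment below 5% myeloid blasts means that "the patient has a sustained CR/CRi and will continue treatment according to this protocol". Section 9.1.3 requires more than 5% marrow blasts without another explanation such as regeneration, and a repeat marrow at least a week later if the share is 5% to 20% with no circulating blasts. Its blood criterion is "The reappearance of circulating blast cells on more than one determination".

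Three other places bear on the consequence. Section 10.1.2 sends all SAEs to the SAE form except for a special situation that it says is described further down but does not identify. Section 10.2.1 asks for all SAEs by fax within 24 hours and names no exception. Section 14 gives the DSMB monthly SAE listings drawn from the safety database.

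**The concern.** The exemption makes sense for patients whose leukaemia has come back, because their infections and bleeds are expected consequences of the disease. The definition does not confine it to them. Any upward movement of the marrow blast count qualifies, at any level and against any earlier marrow, including the rise that section 9.1.3 itself allows for when marrow regenerates. Reappearance of blood blasts qualifies without the second determination that 9.1.3 demands.

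A patient in remission on midostaurin who has a serious infection can therefore carry the label of AML progression. If the investigator attributes the infection to it, the event leaves the expedited route. This misclassification can only take events out of that route and never adds any. In an 18-patient trial whose safety oversight rests on SAE review, a few events handled this way could matter.

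**Working it through.** There is no planned figure to reproduce. The check sets the definitions side by side and applies them to example values.

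**Step 1: marrow criterion.** Rules applied to a change from b0 to b1: progression under 10.2.2 if b1 > b0; marrow in remission under 7.1 and 9.1.1 if b1 < 5%; relapse under 9.1.3 only if b1 > 5%, with its conditions. The blast values are illustrative assumptions.

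| Marrow blasts | 10.2.2 | 7.1 / 9.1.1 | 9.1.3 |
|---|---|---|---|
| 1% to 2% | progression | in remission | not relapse |
| 1% to 4% | progression | in remission | not relapse |
| 2% to 4.5% | progression | in remission | not relapse |
| 1% to 6% | progression | not in remission | relapse after a repeat marrow (no circulating blasts) |
| 1% to 25% | progression | not in remission | relapse, if not explained otherwise |

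The first three rows are the contradiction. The 6% row is less clean, because section 7.1 calls 5% or more at a remission control a relapse without a repeat. The point does not depend on that row.

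**Step 2: blood and extramedullary criteria.** Section 10.2.2 is silent on the number of determinations for blood blasts, so a single sighting is not excluded; 9.1.3 needs more than one. Section 9.1.1 does not allow blood blasts in CR, so the mismatch here is with relapse and not with remission. The chloroma criterion has a counterpart in 9.1.3 (extramedullary leukaemia) and raises no issue.

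**Step 3: when it matters.** Section 10.2.2 separately removes leukopenic fever and infection, and thrombopenic bleeding, from expedited reporting up to day 39 from the start of each chemotherapy cycle. Within that window the progression clause adds little. Maintenance may begin at the earliest on day 36 of the last cycle (section 7.1) and lasts 12 × 28 = 336 days, so at most days 36 to 39, four days, fall inside the window. After that come 9 months of follow-up. Marrows are taken every three months in both phases, and each can show an increase.

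**Step 4: which report is waived.** Section 10.2.2 speaks of expedited reporting and its time lines. Section 10.1.2 has an unidentified exception to the SAE form, and 10.2.1 has none. The exceptions text ends by saying that, for myelosuppression, only the prolonged form needs immediate reporting on an SAE form. This suggests that the exceptions also govern the investigator's form. The three places do not settle whether the form is due for progression-related events, and so do not settle whether such events enter the listings described in section 14.

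**The case against.** The strongest reply is that the exemption is narrow. It covers only the speed and route of reporting, the events stay in the source data and CRF, and section 10.2.1 still asks for every SAE within 24 hours. It is also causal: the text reads, for example, "infections resulting from AML progression". A blast count that moves from 1% to 2% exempts nothing unless the investigator also judges that it caused the event. SUSARs remain reportable within 15 or 7 days, and section 10.1.1 has the investigator document any suspected relationship to the study drugs. All of this stands, and it limits the consequence. It does not remove the contradiction, because the definition supplies the premise on which the attribution is made.

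A reader might infer three stronger things that the documents do not support.

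- That these events are exempt from SAE reporting altogether, or that reported toxicity is understated. Waiver of the SAE form is only one reading of 10.1.2, 10.2.1 and 10.2.2, and the toxicity endpoint in 13.2.2 is the incidence of AEs, for which CRF recording is kept.
- That nearly every patient is affected, because counting error alone will raise a low blast share at some marrow. This describes how often the definition is met. It does not say how often a serious event occurs, is attributed to progression and goes unreported.
- That patients in remission must be withdrawn, because section 6.3 lists "In case of unacceptable toxicity or progressive disease" among the mandatory reasons. The definition in 10.2.2 stands under a reporting heading, and 6.3 does not refer to it. Section 6.3 names refractory disease, hematological relapse and death as the events that end study treatment, which fits section 7.1.

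**Conclusion.** The point holds in limited form. Section 10.2.2 states a definition of AML progression that conflicts with the protocol's own remission and relapse criteria. Under it, a serious event in a patient in sustained CR/CRi can be attributed to progression and left out of expedited reporting. It is still recorded in the source data and CRF. The effect lies mainly in the 336 days of maintenance and the follow-up after it.

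The number of events cannot be estimated: the protocol gives neither a rate of such events nor a rate of attribution to progression. The conclusion rests on reading the definition as written, with no unstated threshold. Whether the SAE form is waived, and whether the DSMB would see these events, remains open on the present text and is part of the finding.

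**What to change.** In section 10.2.2, limit the exemption to events in patients with documented primary refractory disease (sections 9.1 and 13.2.1) or hematological relapse as defined in 9.1.3. This replaces the free-standing definition of progression with terms the protocol already has.

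State consistently in 10.1.2, 10.2.1 and 10.2.2 that these SAEs still go on the SAE form and into the safety database, so that they appear in the DSMB's monthly listings. In 10.1.2, identify the special situation by section number.

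The term progressive disease in 6.3 is undefined and should be reconciled with 7.1 and 9.1.3. No withdrawal rule is proposed here.

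The cost is a short wording change in an amendment and in the SAE guidance to sites, and a few more expedited reports from patients in remission.

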## 7.2.1.3 Midostaurin dose modifications for hematologic toxicity during maintenance treatment

In the presence of grade 4 neutropenia during continuation therapy, midostaurin must be held until ANC  $\geq 1000/\mu$ L. Once ANC  $\geq 1000/\mu$ L, then resume midostaurin at the previous dose. If neutropenia persists for more than two weeks, then discontinue midostaurin protocol therapy.

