## 14 Data Safety Monitoring Board (DSMB)

The DSMB will consist of three members of the scientific community not involved in this trial. The committee will meet to review study data with the National Coordinating Investigator (LKP) of the trial and review all serious adverse events (SAE), and suspected unexpected severe adverse reactions (SUSARs). Meetings will take place approximately every 4-6 months and will receive monthly SAE listings from the safety database between meetings for review as well. The DSMB will give recommendations about the continuation of the trial and/or about necessary trial amendments.

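### Section 10.2.2 exempts cytopenias from AE recording with no phase limit, contradicting section 10.1.1 in midostaurin-only maintenance, and leaves SAE reporting of infection and bleeding up to day 39 unclear

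*Protocol*

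**What the plan says.** **Cytopenias.** The study-specific exceptions in section 10.2.2 say that leukopenia, thrombocytopenia and anemia "are intended and expected events during treatment of AML" and "do therefore not fulfil criteria of adverse events and do not need to be documented as AEs or SAEs". No phase, grade, duration or relatedness is specified. One case is brought back: "In this context only prolonged myelosuppression, i.e. pancytopenia with marrow hypocellularity on day 40 or later from start of last cytotoxic therapy" goes on an SAE form at once, provided that leukemia is not evident.

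**Infection and bleeding.** The same section says: "Myelosuppression-associated complications and related hospitalizations must be reported on appropriate pages of the CRF as an adverse event but are excluded from expedited reporting". This covers fever and infection from leukopenia and bleeding from thrombopenia, from the start of each chemotherapy cycle to day 39. Fatal or life-threatening outcomes are not mentioned.

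**General rules.** Section 10.1.1 requires any change in laboratory findings "which leads to the discontinuation of the subject's treatment with the investigational medicinal product" always to be recorded as an AE. Section 10.1.2 sends serious AEs to the SAE form, except for a special situation that it places further on without identifying it. Section 10.2.1 requires all SAEs to be faxed within 24 hours and names no exception.

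**Maintenance.** Section 7.2.1.3 holds midostaurin for grade 4 neutropenia and adds: "If neutropenia persists for more than two weeks, then discontinue midostaurin protocol therapy".

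**Use of the data.** Section 13.2.2 makes toxicity a secondary target variable, measured as AE incidence. Under section 14 the DSMB reviews study data, SAEs and SUSARs about every 4-6 months and receives monthly SAE listings in between. Section 13.6 plans no interim analysis.

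**The concern.** The reason given for the cytopenia exemption is that low counts are an intended effect of AML treatment. That is sound while cytarabine or daunorubicin is being given. In maintenance there is no cytotoxic drug, so a new low count is either a possible effect of midostaurin or a sign of disease. Following section 10.2.2 as worded, a site need not record it as an AE.

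Two things are at stake. First, the toxicity endpoint of a trial that adds midostaurin to standard therapy would leave out one class of possible midostaurin effects by definition, in the phase where attribution is cleanest. Second, the sections on serious events give sites conflicting instructions about infection and bleeding during chemotherapy cycles. A site that takes the exceptions literally could keep a fatal neutropenic infection off the form that feeds the DSMB's monthly listing.

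**Working it through.** No figure in the plan is in dispute. The check sets the rules side by side and counts days.

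**1. Share of midostaurin exposure outside chemotherapy cycles** (sections 4.3 and 7.1)
- With chemotherapy: days 8-21 is 14 days per cycle, with one induction and three consolidation cycles: 4 × 14 = 56 days.
- Maintenance: 12 cycles × 28 days = 336 days.
- Share in maintenance: 336 / (56 + 336) = 336 / 392 = 85.7%.

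This is planned exposure for a patient who completes treatment.

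**2. Does the reason for the exemption hold in maintenance?** The protocol's own text suggests not.
- Section 2.2 reports a lack of myelosuppression with midostaurin in solid tumor patients.
- Section 3.3 describes the drug as non-cytotoxic.
- Section 7.1 requires ANC of at least 1000/µL and platelets of at least 50,000/µL before maintenance starts, so a later grade 4 neutropenia is a new event.
- Section 8.4.2 lists anemia and leukopenia among the SAEs considered related to midostaurin.

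**3. Cytopenia in maintenance under each rule**

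| Event | Section 10.1.1 | Section 10.2.2 |
|---|---|---|
| Neutropenia that ends midostaurin (7.2.1.3) | Always an AE | Not an AE |
| Neutropenia that leads only to a hold (7.2.1.3) | Within the general AE definition, but not within the discontinuation rule | Not an AE |
| Pancytopenia with hypocellular marrow, day 40 or later | AE | SAE form at once |

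The first row is a direct contradiction. In the second row the discontinuation rule gives no protection, so the exemption removes the event from AE incidence. The third row needs pancytopenia and a marrow finding, so isolated neutropenia does not meet it.

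**4. Infection and bleeding**
- The window runs from day 1 to day 39 of each chemotherapy cycle. Midostaurin days 8-21 lie inside it, so all 56 midostaurin days given with chemotherapy are covered.
- Maintenance may start on day 36 of the last cycle, so the overlap is at most days 36-39: 39 − 36 + 1 = 4 days, and 4 / 336 = 1.2%. This exemption barely touches maintenance.
- Section 10.2.1 requires all SAEs within 24 hours. Section 10.1.2 excepts a special situation, and the closing sentence of the exceptions in section 10.2.2 says that only prolonged myelosuppression needs immediate reporting on an SAE form. A fatal neutropenic infection on day 15 of a consolidation cycle is therefore due within 24 hours on one reading and is only a CRF adverse event on the other.

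**5. The schedule.** In the tables in the visit schedule and section 7.4, the AE row is marked at the start of maintenance and is then empty, while the SAE row says monthly. Section 10.1.1 wants AEs documented until 30 days after the last dose. Merged cells may have been lost in the text at hand, so this needs only a check.

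**The case against.** A reader might infer three stronger conclusions. The text does not support them.

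**That cytopenias are never adverse events.** Prolonged pancytopenia with a hypocellular marrow is reportable on an SAE form, with no end date, so that exception reaches into maintenance. Section 10.1.1 independently makes a cytopenia that ends midostaurin an AE. The defect is a contradiction and a missing limit, not a total exemption.

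**That fatal neutropenic infections are exempt from SAE reporting.** The text says only that these complications "must be reported on appropriate pages of the CRF as an adverse event but are excluded from expedited reporting". The clause sits under the sponsor's duties, where expedited reporting means the 7- and 15-day timelines, and the investigator's 24-hour rule in section 10.2.1 is unqualified. Fatal SUSARs and an increased incidence of expected serious reactions also remain reportable. This is a fair reading. However, the SAE form is the investigator's instrument, and the closing sentence of the exceptions reserves its immediate use for prolonged myelosuppression. Together with the exception in section 10.1.2, that supports the opposite reading too. The text is ambiguous.

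**That the main toxicities are hidden from the DSMB.** The DSMB also reviews study data. Blood counts are a named safety parameter in section 9.2, taken twice weekly in chemotherapy cycles and monthly in maintenance. Every death is an EFS event, and section 9.2 uses EFS for safety as well. Section 8.4.2 names nausea, vomiting and fatigue as the most frequent midostaurin effects. What remains is possible delay or absence in the monthly SAE listings between meetings. The documents give no rate of toxic death, so no percentage of missed deaths can be derived.

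It could also be said that collecting blood counts makes AE recording of cytopenias redundant. It does not, because the endpoint is defined by AEs and not by laboratory values.

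**Conclusion.** The point holds in two parts.

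The cytopenia clause is worded too broadly. It applies through all of midostaurin-only maintenance (86% of planned midostaurin days), contradicts section 10.1.1 read with section 7.2.1.3, and lowers the AE-based toxicity endpoint by construction. Neutropenia that leads only to a hold is the clearest loss. The 86% assumes full treatment. It is a share of exposure time, not of missed events, whose number cannot be estimated from the protocol.

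The handling of serious infection and bleeding up to day 39 is unclear. Sections 10.1.2 and 10.2.2 do not agree with section 10.2.1, and fatal outcomes are not carved out. The events stay in the CRF, and deaths stay in the primary endpoint. The risk is confined to timeliness and completeness of the DSMB's SAE listings. With meetings 4-6 months apart and no interim analysis, those listings are the committee's only scheduled information between meetings.

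This should be corrected. It does not affect the primary analysis or the sample size.

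**What to change.** Change recording and reporting only:

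1. In section 10.2.2, limit the cytopenia exemption to the window already used for infection and bleeding, from the start of each chemotherapy cycle to day 39.
2. State that in maintenance a cytopenia that leads to a hold or discontinuation of midostaurin is recorded as an AE.
3. State that fatal and life-threatening events fall outside all the reporting exceptions, go on the SAE form within 24 hours and enter the DSMB listing.
4. Reconcile sections 10.1.1, 10.1.2, 10.2.1 and 10.2.2. Section 10.1.2 should name the special situation it means, and section 10.2.1 should refer to it.
5. Check the AE row of the visit schedule during maintenance against section 10.1.1.

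No dose, hold or stopping rule is altered. The cost is a few sentences, possibly one table entry, and a few more AE and SAE forms. The monthly visits and blood counts in maintenance are already scheduled.
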